3.5.3 Safety assessments

The incidence of AEs will be tabulated and reviewed for potential signals and clinical importance. The most prevalent AEs will be reported by group: (AL → AQ → AL + AQ) vs (AQ → AL → AL + AQ). Any Serious Adverse Events (SAEs) including any deaths will also be reported by group. Standard haematological parameters, serum chemistries, liver and renal function test results at screening and post-treatment will be summarised across the treatment groups. For the safety data such as adverse events, proportions will be compared using Fisher's exact test and a significance level of 5% where appropriate.

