11.4 Evaluating Adverse Events and Serious Adverse Events

11.4.1. Assessment of Intensity

All adverse events will be evaluated by the investigators and graded according to Common Terminology Criteria for Adverse Events (CTCAE) version 5.0. For lab results that are not available in Common Terminology Criteria for Adverse Events (CTCAE) version 5.0, the investigator should make a determination as to whether or not the laboratory abnormality is clinically significant. If PI believes lab abnormality is clinically significant, it should be reported as an adverse event and a grade should be identified to the best of their ability.

If an adverse event is not listed in the Common Terminology Criteria for Adverse Events (CTCAE) version 5.0, the Investigator will assess the severity using the following guidelines:

1 = Mild: asymptomatic or mild symptoms; clinical or diagnostic observations only; intervention not indicated.

2 = Moderate: minimal, local or non-invasive intervention indicated; limiting age appropriate instrumental ADL*

3 = Severe or medically significant but not immediately life-threatening; hospitalization or prolongation of hospitalization indicated; disabling; limiting selfcare ADL**

4 = Life-Threatening consequences; urgent intervention indicated

5 = Death related to AE

Activities of Daily Living (ADL)

*Age-appropriate instrumental ADL which will be defined in study SOPs.

**Age-appropriate self-care ADL which will be defined in study SOPs.

Clarification of the difference in meaning between "severe" and "serious"

The term "severe" is often used to describe the intensity (severity) of a specific event (as in mild, moderate, or severe myocardial infarction); the event itself, however, may be of relatively minor medical significance (such as severe headache). This is not the same as "serious", which is based on the outcome or criteria defined under the serious adverse event definition. An event can be considered serious without being severe if it conforms to the seriousness criteria, similarly severe events that do not conform to the criteria are not necessarily serious. Seriousness (not severity) serves as a guide for defining regulatory reporting obligations.

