12.5.2 Safety Analysis

Safety analyses will be based on the safety set. Safety and tolerability of artemether, lumefantrine and amodiaquine will be assessed by comparing the frequency (%) of adverse events and serious adverse events, with particular attention to abdominal pain, appetite perturbation and QT interval prolongation, using the Fisher's exact test. Safety data will be presented in tabular and/or graphical format and summarized descriptively. Any clinically relevant abnormalities or values of potential clinically concern will be described. Subjects will be analysed as treated.

An additional exploratory analysis evaluating independent renal markers against standard blood urea nitrogen/ creatinine levels will be conducted using appropriate statistical methods.

Adverse Events

All adverse event summaries will refer to treatment emergent adverse events, i.e. adverse

events that newly started or increased in intensity after the study drug administration. AE summaries will be generated for all AEs that occurred after study drug administration, until the end of the study.

12.6 Assessment of the relationship between pharmacokinetic parameters and ECG findings.

In addition to the results of the safety analysis, an exploratory analysis of the ECG data will be conducted. The ECG parameters will be compared with the PK properties of the drugs using appropriate statistical methods.

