13.2. Risks

Artemether-lumefantrine

Reported Artemether-lumefantrine side effects have generally been mild. The common side effects are headache (56%), anorexia (40%), dizziness (39%), asthenia (38%), GI disorders (loss of appetite 40%, nausea 26%, vomiting 17%, abdominal pain 17%), arthralgia (34%), myalgia (32%), sleep disorder (22%), palpitations (18%), fatigue (17%). Rare but could be serious side effects are hepatomegaly (9%) and anemia (4%).

Amodiaquine

The main side effects of amodiaquine are nausea, vomiting and fatigue which are mild to moderate in nature. Transient sinus bradycardia and QTc prolongation were reported in malaria patients treated with amodiaquine (16 and 7 of 20 patients, respectively), but did not result in any symptoms (Ngouesse et al., 2001). Transient neurological problems were reported in drug overdose. When the drug was used for a long period such as in malaria prophylaxis (now not recommended), rare adverse reactions of agranulocytosis (1:2000-2200), hepatoxicity (1:15600), yellow pigmentation, and ocular changes including irreversible retinal abnormalities were observed.

Risk of Blood Collection

Sample blood taking may cause some pain, bleeding and bruising. Rarely, a local skin infection may develop. Occasionally, a subject may feel lightheaded or faint when blood is drawn. Blood for the pharmacokinetic study will be drawn via an indwelling catheter whenever possible to minimize the number of venipunctures.

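### Adverse events are compared by incidence only, and the SAP groups them by sequence, so greater intensity under AL+AQ does not appear in the planned comparison

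*SAP*

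**What the plan says.** - **Adverse event analysis, SAP 3.5.3.** "The incidence of AEs will be tabulated and reviewed for potential signals and clinical importance". The most prevalent events and the serious events are reported by sequence (AL then AQ then AL+AQ, against AQ then AL then AL+AQ). Proportions are compared with Fisher's exact test "and a significance level of 5% where appropriate". SAP 3.1 says the same of proportions in general.
- **Adverse event analysis, protocol 12.5.2.** Safety is assessed by "comparing the frequency (%) of adverse events and serious adverse events, with particular attention to abdominal pain", appetite perturbation and QT prolongation, again with Fisher's exact test. It does not state which groups form the columns, but it does say that subjects are analysed as treated.
- **Grading, protocol 11.4.1.** "All adverse events will be evaluated by the investigators and graded according to Common Terminology Criteria for Adverse Events (CTCAE) version 5.0". For events that are not listed there, "the Investigator will assess the severity using the following guidelines", which is a scale from 1 to 5. Every adverse event should therefore carry a grade.
- **Use of grade or intensity.** Grade enters the halting rule in protocol 10.4. A rise in intensity can make an event count as treatment-emergent in protocol 12.5.2. No table, maximum grade per subject or comparison by grade is planned in either document.

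**The concern.** Safety and tolerability of the co-administered drugs is a secondary objective (protocol 2.2, SAP 2.3). The question is whether AL+AQ is less well tolerated than AL or AQ alone in the same people. Two features of the plan stand in the way.

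First, incidence counts a subject with a mild headache and a subject with a severe one identically. If a subject has the event on AL alone and again, but worse, on AL+AQ, nothing changes in the count.

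Second, the SAP's columns are sequences, and every subject in both sequences ends with AL+AQ. An effect of the combination falls in both columns alike, so a contrast between them does not estimate it, by incidence or by intensity.

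At stake is a report of no difference in adverse events that says nothing about how bad the events were, although the protocol requires that information for each one.

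**Working it through.** The documents give no expected adverse event rate and no figure for the safety comparison, so there is nothing to reproduce. The counts below are illustrations.

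**Inputs.** 16 subjects, 8 per sequence, each planned to receive all three regimens (protocol section 4). Fisher's exact test at 5% (SAP 3.5.3); sidedness is not stated, and two-sided is assumed.

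**Step 1: incidence by regimen, same subjects affected.** Suppose *a* of 16 have an event on the single regimen and the same *a* have it on AL+AQ. Fisher's test on *a*/16 against *a*/16 gives p = 1.00 for *a* = 4, 6, 8, 10 and 12. The grades do not enter, so any number of them may worsen.

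**Step 2: incidence by sequence, as the SAP groups it.** With equal incidence in the two sequences, *a*/8 against *a*/8 gives p = 1.00 for *a* = 2, 4 and 6.

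**Step 3: grade added, sequence columns kept.** Suppose AL+AQ produces events of grade 2 or above in half of each sequence: 4/8 against 4/8 again gives p = 1.00. Adding grade without changing the columns does not help.

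**Step 4: grade and regimen together.** Suppose *k* of 16 subjects move from grade 1 on the single regimen to grade 2 or above on AL+AQ, and none moves the other way. For grade 2 or above this is 0/16 against *k*/16.

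- Fisher, two-sided: p = 2 × C(16,*k*)/C(32,*k*). For *k* = 5: 2 × 4368/201376 = 0.043.
- Paired exact (McNemar): p = 2 × 0.5^*k*. For *k* = 6: 2 × 0.015625 = 0.031.

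| Shifts *k* | Any-grade incidence | Grade 2+, Fisher | Grade 2+, paired exact |
|---|---|---|---|
| 4 | 1.00 | 0.101 | 0.125 |
| 5 | 1.00 | 0.043 | 0.063 |
| 6 | 1.00 | 0.018 | 0.031 |
| 8 | 1.00 | 0.0024 | 0.0078 |

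The paired column is the one to read, because the same subjects supply both proportions. Six shifts in one direction are 6/16 = 37.5% of the trial, so the table by grade would show a pattern well before a test did.

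**The case against.** **Much of severity is covered elsewhere.** Serious events are reported separately, laboratory results are summarised, ECG parameters have an exploratory analysis against pharmacokinetics (protocol 12.6), clinically relevant abnormalities are to be described, and grade 3 or above events judged related feed the halting rule. This stands, and it narrows the point to non-serious symptoms. It does not remove it: protocol 11.4.1 itself says that severe is not the same as serious, the halting rule is silent on a move from grade 1 to grade 2, and a general review for clinical importance is not a specified summary.

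**The SAP is brief.** It has table shells for baseline and pharmacokinetics but none for adverse events, so a missing grade column may be brevity. That is fair, but the sequence grouping is stated explicitly.

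**A reader might infer that the incidence test is nearly powerless and a grade-based test far better.** The documents do not support that. Simulations of 16 paired subjects, with assumed within-subject latent correlation of 0.3 to 0.6, do give about 1% significance for any-grade incidence against 59–64% for a paired test of grade 2 or above. But that result holds any-grade incidence at 56% on both regimens while grade 2 or above rises from 10% to 50%, and nothing in the documents says that incidence would stay fixed. If the whole severity scale shifts instead, Fisher's test on any grade by regimen reaches about 54% against 59–63%. For a rise from 10% to 30% it does better than the grade test (17–19% against 10–11%).

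**A reader might also infer that incidence has no room to rise.** From the AL side-effect rates in protocol 13.2, 1 − 0.44 × 0.60 × 0.61 × 0.62 = 0.90 would have at least one of the four commonest effects. That assumes the symptoms are independent. The same rates are compatible with any value from 56% upwards, and section 13.2 does not state the population for them.

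**Conclusion.** The point holds as a gap in a planned secondary analysis. The adverse event comparison is by incidence only, and the SAP's grouping by sequence cannot separate AL+AQ from the single regimens. A rise in intensity among subjects who also have the event on AL or AQ alone, from mild to moderate or to severe but not serious, leaves that comparison unchanged (p = 1.00 in every case worked above). This follows from the definition of incidence and needs no assumption about rates.

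The size is modest. The primary pharmacokinetic analysis is unaffected, and the gap lies mainly in non-serious symptomatic events. No general gain in power should be claimed for grade over incidence: which does better depends on whether added toxicity raises intensity alone or frequency as well, and the documents do not settle that. With 16 subjects the grade comparison can only be descriptive. AL+AQ is also always given last, so a within-subject difference carries any period effect with it.

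**What to change.** In SAP 3.5.3:

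1. Tabulate adverse events by regimen received (AL, AQ, AL+AQ) instead of by sequence.
2. For any adverse event, and for the events named in protocol 12.5.2 (abdominal pain, appetite perturbation, QT prolongation), show the number of subjects by maximum grade: none, 1, 2, 3 or above. Keep any-grade incidence alongside.
3. Report the within-subject difference between AL+AQ and each single regimen, for any grade and for grade 2 or above, with an exact paired confidence interval. State that these are descriptive and serve signal detection.
4. State how an event is assigned to a regimen and over what window, since scheduled follow-up runs to day 28 after AL but to day 42 after AQ and AL+AQ.

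**Cost.** SAP wording, one more table and a few more comparisons of low precision. The protocol already requires grading, so no new assessment is needed, but the documents do not list the case report form fields; confirm that grade and onset date are recorded for each event. No clinical rule changes.

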Amodiaguine by oral administration is absorbed rapidly, and then extensively metabolized to N-desethylamodiaquine (active metabolite) and 2-hydroxy-desethyl-amodiaquine by hepatic first-pass effect. C_{max} of amodiaguine in plasma, whole blood and packed cells is 32±3ng/ml, 60±10ng/ml and 42±6ng/ml respectively; Tmax of amodiaguine is 0.5±0.03h, 0.5±0.1h and $0.5\pm0.1h$ respectively; AUC₀₋₈ of amodiaguine in plasma, whole blood and packed cells is 99 ± 19 ng·ml⁻¹h, 148 ± 25 mJ⁻¹h and 167 ± 72 ng·ml⁻¹h respectively. Cmax of desethylamodiaguine in plasma, whole blood and packed cells is 181±26ng/ml (19 fold higher than those of the parent drug), 561±70ng/ml and 561±143ng/ml respectively; Tmax for desethylamodiaguine is 3.4±0.8h, 2.2±0.5h and 3.6±1.1h respectively; and AUC0-24 for desethylamodiaquine in plasma, whole blood and packed cells is 2304±37ng·ml⁻¹h, 6811±752ng·ml⁻¹h and 5713±1269ng·ml⁻¹h respectively (whole blood AUC was higher than plasma AUC, P<0.001). The trial of ¹⁴C-labelled amodiaquine administered orally to Wistar rats showed that amodiaquine can be distributed widely in body with the main organs of accumulation being kidney, liver, bone marrow and spleen. Amodiaquine is not observed in plasma 8 hours after administration, whereas the concentration of desethylamodiaquine in plasma at 96h is 29 ± 8 ml⁻¹. The half-life of amodiaguine in plasma is 5.2 ± 1.7 h, and elimination half-life ($\beta_{t1/2}$) of desethylamodiaquine in plasma is 9-31 days. The bioavailability of amodiaquine is decreased due to first-pass hepatic metabolism. The plasma protein binding rate of amodiaguine and desethylamodiaguine is greater than 90%. The T_{max} of amodiaguine taken orally by patients with falciparum malaria is 1.75h, distinctly longer than the T_{max} of healthy volunteers (18).

Potential interactions through hepatic metabolism

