4. STUDY DESIGN

This is an open-label pharmacokinetic study in 16 healthy Thai subjects. Subjects will be admitted in the inpatient ward and will be randomized to **group A** or **group B** to receive 3 drug regimens described in the following table 1. Every subject will have 1 screening and 3 admissions in the hospital.

Visit 1	Screening					
	Within 14 days					
	Group A (n = 8)	Group B (n = 8)				
Visit 2	Regimen 1	Regimen 2				
	Artemether-lumefantrine	Amodiaquine				
	on Day 0, 1, and 2	on Day 0, 1 and 2				
	Washout period: > 6 we	eeks (after day 3)				
Visit 3	Regimen 2	Regimen 1				
	Amodiaquine	Artemether-lumefantrine				

 Table 1: Study Schedule

	on Day 0, 1 and 2	on Day 0, 1 and 2		
Washout period: > 6 weeks (after day 3)				
Visit 4	Regimen 3			
	Artemether-lumefantrine + Amodiaquine on Day 0, 1 and 2			

The total duration for each subject's participation in the study is approximately 6 - 8 months depend on washout period. Study duration is approximately 12 months.

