2.3 SECONDARY OBJECTIVES

- a. To characterize the pharmacokinetic properties of artemether-lumefantrine and amodiaquine when given alone and in combination.
- b. To evaluate the safety and tolerability of co-administered artemether-lumefantrine and amodiaquine. Protocol version 6.0 dated 22 June 2022 10 of 42.
- c. To investigate pharmacogenetic polymorphisms affecting drug levels of artemetherlumefantrine and amodiaquine and their metabolites.

STATISTICAL ANALYSIS PLAN FOR ALAQ STUDY

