2.5 GENERAL

This is an open-label pharmacokinetic study in 16 healthy Thai subjects. Subjects will be admitted in the inpatient ward and will be randomized to Artemether-lumefantrine followed by Amodiaquine or Amodiaquine followed Artemether-lumefantrine. There will be a washout period: > 6 weeks (after day 3) and then each of the participants will be given Artemether-lumefantrine + Amodiaquine. Thus, eEvery subject will have 1 screening and 3 admissions in the hospital.

All subjects will undergo screening assessments (visit 1). Screening assessments (visit 1) may be carried out over more than one day, provided that all required assessments are completed within the 14 days prior to visit 2. If the interval between screening (visit 1) and day -1 visit 2 is three days or less, the clinical laboratory screening test result and serum pregnancy test result can be used for enrolment evaluation on day -1 visit 2. In such cases, these tests would not need to be repeated at day1 visit 2

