3.5.2 Pharmacokinetic assessments

Individual pharmacokinetic parameters of artemether/dihydroartemisinin, lumefantrine/desbutyl-lumefantrine and amodiaquine/desethylamodiaquine will be calculated after each dose administration using a non-compartment approach.

Total exposure up to the last measured concentration (AUC_{LAST}) will be calculated using the linear trapezoidal method for ascending concentrations and the logarithmic trapezoidal method for descending concentrations. The terminal elimination half-life ($t_{1/2}$) will be estimated by the slope (λ_Z) of the best-fit log-linear regression of the observed concentrations in the terminal elimination phase. Drug exposure will be extrapolated from the last observed concentration to time infinity by C_{LAST}/λ_Z for each individual subject to compute total drug exposure (AUC_{∞}). Maximum concentration (C_{MAX}) and time to maximum concentration (T_{MAX}) will be taken directly from the observed data. Apparent oral elimination clearance (CL/F) and apparent volume of distribution (V/F) will be computed individually according to the equations below.

$$CL/F = \frac{Dose}{AUC_{\infty}} \quad V/F = \frac{t_{1/2} \times CL/F}{\ln 2}$$

The pharmacokinetic parameters will be summarised for each drug stratified by arm (i.e., when administered alone or in combination). Similarly, descriptive statistics will be summarised by arm. Ln-transformed pharmacokinetic exposure parameters (C_{MAX} , AUC_{LAST} and AUC_{∞}) will be evaluated to assess potential drug-drug interactions. No drug-drug interaction is assumed if the 90% confidence intervals of the ratio (combination/alone) of C_{MAX} , AUC_{LAST} and AUC_{∞} fall within 80% to 125% [10]. The 90% confidence intervals of the ratio (combination (COMB)/alone (ALONE)) will be calculated according to equation below.

$$Mean\ ratio\ (\%) = 100 \cdot e^{Parameter_{combination} - Parameter_{alone}}$$

where $Parameter_{combination}$ and $Parameter_{alone}$ are the least square mean of the natural logarithm of parameters derived for the combination and alone administration, respectively. The upper and lower boundary of the 90% confidence interval are calculated as follow:

$$90\% \ Confidence\ Interval = 100 \cdot e^{(Parameter_{combination} - Parameter_{alone}) \pm t_{0.95} \cdot SE_D}$$

STATISTICAL ANALYSIS PLAN FOR ALAQ STUDY

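### The only adverse-event contrast the SAP names compares two sequences that both contain the combination, so it does not address co-administration safety

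*SAP*

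**What the plan says.** The secondary safety objective, in the same terms in Protocol 2.2 and SAP 2.3, is "To evaluate the safety and tolerability of co-administered artemether-lumefantrine and amodiaquine".

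The design gives every subject every regimen. Sixteen subjects are randomised, 8 per sequence, to AL then AQ or to AQ then AL. After a further washout, "each of the participants will be given Artemether-lumefantrine + Amodiaquine" (SAP 2.5; Protocol section 4, Table 1).

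SAP 3.5.3 says "The most prevalent AEs will be reported by group" and writes the groups out as the two full sequences. It adds: "Any Serious Adverse Events (SAEs) including any deaths will also be reported by group". Fisher's exact test at 5% is to be used where appropriate. The section also promises a tabulation of adverse-event incidence, without saying how it is stratified, and a laboratory summary across treatment groups that it does not define.

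Protocol 12.5.2 assesses safety "by comparing the frequency (%) of adverse events and serious adverse events", again with Fisher's test and on an as-treated basis. It does not say which groups are compared.

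The pharmacokinetic section does specify the split that matters: "The pharmacokinetic parameters will be summarised for each drug stratified by arm (i.e., when administered alone or in combination)" (SAP 3.5.2).

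**The concern.** The SAP states one explicit comparison for adverse events and serious adverse events, and it is between randomised sequences. The sequences differ only in the order of AL and AQ. AL+AQ is given third in both, so its events enter both columns alike.

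A reader who sees similar columns could take them as reassurance about the combination, when they carry no information on it. The comparison that speaks to the objective, AL+AQ against each drug alone in the same subjects, has no table or method in the SAP. If it is added later, the event windows, the attribution rule and the choice of test will be settled after the data have been seen.

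Fisher's test is valid for an 8 v 8 sequence contrast. The difficulty lies in what is being compared.

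**Working it through.** The documents give no power or error rate for the safety comparison, so there is no plan figure to reproduce. The group sizes (8 per sequence, 16 in all) are from Protocol section 4. All adverse-event risks below are assumptions.

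**1. Expected columns by sequence.** Let a, q and c be the risks of an adverse event in the AL, AQ and AL+AQ periods, with no order or carry-over effect. Expected subject-periods with an event are:

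- Group A: 8 × (a + q + c)
- Group B: 8 × (q + a + c)

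The difference is 0 for every value of a, q and c. With a = q = 0.2:

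| AL+AQ risk | Group A | Group B | By regimen, of 16: AL / AQ / AL+AQ |
|---|---|---|---|
| 20% | 8 × 0.6 = 4.8 | 4.8 | 3.2 / 3.2 / 3.2 |
| 50% | 8 × 0.9 = 7.2 | 7.2 | 3.2 / 3.2 / 8.0 |
| 80% | 8 × 1.2 = 9.6 | 9.6 | 3.2 / 3.2 / 12.8 |

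**2. The same result as a subject proportion, which is what Fisher's test uses.** P(any event) = 1 − (1 − a)(1 − q)(1 − c) in both sequences, with periods independent. With a = q = 0.1 and two-sided tests at 5%:

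| AL+AQ risk | P(any event), each sequence | Fisher 8 v 8 rejects | Exact McNemar, AL+AQ v AL, n = 16, rejects |
|---|---|---|---|
| 10% | 27.1% | 1.0% | 0.1% |
| 30% | 43.3% | 2.0% | 11% |
| 50% | 59.5% | 1.9% | 54% |
| 70% | 75.7% | 0.7% | 91% |
| 90% | 91.9% | 0.02% | 99.8% |

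At any common rate the 8 v 8 Fisher test rejects at most 2.13% of the time (at a rate of 0.5), and every such rejection is a false positive. McNemar power uses discordant probabilities c(1 − a) and a(1 − c).

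**3. Carry-over.** Protocol section 1 says the elimination half-life "of desethylamodiaquine in plasma is 9-31 days" and gives 3 to 6 days for lumefantrine. Table 1 has "Washout period: > 6 weeks (after day 3)". Assuming mono-exponential decline, the fraction left after 42 days is 2^(−42/half-life):

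- desethylamodiaquine: 2^(−42/9) = 3.9% to 2^(−42/31) = 39%
- lumefantrine: at most 2^(−42/6) = 0.8%

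The period straight after AQ is AL+AQ in Group A and AL in Group B. Assume carry-over adds 20 points there, with a = q = c = 0.2. Each column then expects 8 × (0.6 + 0.2) = 6.4 subject-periods, so the totals still match. The effect shows only when regimen is split within sequence: AL has 8 × 0.2 = 1.6 of 8 in Group A and 8 × 0.4 = 3.2 of 8 in Group B. That equality of totals belongs to the subject-period count; the subject-level count is taken up with the objections.

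**The case against.** **The protocol already implies a by-regimen analysis.** An as-treated rule means little when everyone takes everything, unless it refers to the regimen received. Protocol 12.3 also presents numbers by study drug group, and SAP 3.5.2 splits by alone or combination. On this reading the defect is a missing table shell in a small study where safety is secondary. Part of this stands: nothing forbids the right analysis. But Protocol 12.3 concerns disposition, SAP 3.5.2 concerns pharmacokinetics, and the as-treated rule names no table or contrast. The SAP also does more than omit detail, because it states a specific comparison that does not serve the objective.

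**Under carry-over the sequence contrast does move.** This is correct for subjects with any event. With a = q = 0.2 and the same 20 points of carry-over, the expected counts of 8 are:

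- Group A: 8 × [1 − 0.8 × 0.8 × (0.8 − c)]
- Group B: 8 × [1 − 0.8 × 0.6 × (1 − c)]

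These give 4.93 v 4.93 at c = 20%, 6.46 v 6.08 at 50% and 8.00 v 7.23 at 80%. The shift mixes carry-over with combination risk, so it is not a usable measure of either, and the main claim is already conditional on no order or carry-over effect.

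**The by-regimen comparison is itself imperfect.** It is confounded with period, blurred by carry-over and low in power. All of that stands, and it is why the display should be descriptive with its limits stated.

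**Conclusion.** The point holds and should be fixed, although it does not threaten the primary pharmacokinetic analysis. The adverse-event and serious-adverse-event contrast in SAP 3.5.3 has an expected difference of exactly zero for any combination risk, provided there is no order or carry-over effect. That result does not depend on the assumed rates; they serve only as illustration. The objective is not lost, since the data are collected and overall incidence is reviewed, but the display that would address it is not specified.

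Sixteen subjects limit what any by-regimen test can show. With within-subject independence, exact McNemar reaches 80% power only when the AL+AQ risk is about 63%, 75% or 92% against single-regimen risks of 10%, 20% or 40%.

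**What to change.** In SAP 3.5.3:

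- Make adverse-event and serious-adverse-event tables by regimen at onset (AL, AQ, AL+AQ) the main safety display, assigning each event to the most recent regimen started.
- Keep the by-sequence table as supplementary, split by regimen within sequence, so that AL given first (Group A) can be read beside AL given after AQ (Group B).
- Show a common day 0–28 table beside the full listing, because scheduled follow-up ends at day 28 after AL but at day 42 after AQ and AL+AQ (Protocol 6.1.2).
- Present the regimen comparison descriptively. If a test is reported, use a paired one such as exact McNemar, since the same 16 subjects appear under every regimen. Fisher's test can stay for the sequence contrast.
- State the limits: AL+AQ is always last and open-label, so regimen is confounded with period; desethylamodiaquine may persist into the period after AQ; and only large differences are detectable.

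The cost is SAP wording and table shells, with no new data. The day 0–28 table leaves out later events, which remain in the full listing, and attribution to the latest regimen can still be blurred by carry-over.

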Abnormal laboratory findings (e.g., biochemistry, hematology, urinalysis) or other abnormal assessments (e.g., BP, RR, BT, HR and ECGs) detected during the study or are present at baseline and worsen following the start of the study will be reported as AEs or SAEs.

Subjects with an adverse event will be managed clinically. This may include stopping study

drug, further investigations, treatment, referral to a specialist, etc.

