2.4 SECONDARY ENDPOINTS

- a. Elimination clearance (CL/F), terminal elimination half-life (t_{1/2}) and apparent volume of distribution (V_d) of artemether, lumefantrine and amodiaquine and their metabolites when given alone and in combination.
- b. Safety and tolerability parameters, including adverse events, electrocardiographic changes, vital signs and biochemical assessments. •
- c. Pharmacogenetic polymorphisms in the case of unusual metabolizeStudy design

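### SAP 3.5.3 splits adverse events by randomised sequence rather than by regimen, and specifies no summary of ECG or vital signs

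*SAP*

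**What the plan says.** The safety objective in SAP 2.3b is "To evaluate the safety and tolerability of co-administered artemether-lumefantrine and amodiaquine". SAP 2.4b defines the matching secondary endpoint as safety and tolerability parameters, "including adverse events, electrocardiographic changes, vital signs and biochemical assessments".

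SAP 3.5.3 is the only SAP section that analyses safety. It does four things:
- It tabulates AE incidence and reviews it for signals, naming no split.
- It then says "The most prevalent AEs will be reported by group: (AL → AQ → AL + AQ) vs (AQ → AL → AL + AQ"), and reports SAEs by the same groups.
- It summarises laboratory results at screening and after treatment.
- It compares proportions such as AEs by Fisher's exact test at 5%, naming no other grouping.

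ECG, QTc, Holter and vital signs are not mentioned there.

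On the design, SAP 2.5 says that after the two single-regimen periods "each of the participants will be given Artemether-lumefantrine + Amodiaquine". For the pharmacokinetics, SAP 3.5.2 summarises parameters "stratified by arm (i.e., when administered alone or in combination").

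The protocol adds three things. Section 11.2 makes abnormal laboratory results "or other abnormal assessments (e.g., BP, RR, BT, HR and ECGs) detected during the study" reportable as AEs or SAEs. Section 12.5.2 compares AE frequencies "with particular attention to abdominal pain, appetite perturbation and QT interval prolongation" and adds "Subjects will be analysed as treated". Section 12.6 plans an exploratory comparison of ECG parameters with PK, with the method left open.

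**The concern.** The groups in SAP 3.5.3 are spelled out as the two sequences, so group cannot be read there as regimen. A subject in either column has taken AL alone, AQ alone and the combination. An adverse effect of the combination raises the event rate in both columns equally and cancels from the comparison. The PK section of the same SAP makes the alone-versus-combination split that safety lacks.

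Two things are at stake. A table with near-equal columns and a non-significant p-value could be read as reassurance about AL+AQ, when it carries no information on that question. And the ECGs, done in triplicate with a full Day -1 profile in each period (protocol 6.3.3 and Table 2), have no stated analysis in the SAP even though they serve a listed endpoint. QT prolongation is one of three events that the protocol singles out.

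**Working it through.** The documents give no figure for this comparison, so there is nothing to reproduce. The structural result comes first and needs no event rates. The numbers after it are illustrations.

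**1. Expected difference between the columns.** Let pAL, pAQ and pC be the probabilities that a subject has the event on AL, AQ and AL+AQ. With independent periods and no order or carry-over effect, in either sequence:

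P(any event) = 1 − (1 − pAL)(1 − pAQ)(1 − pC).

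The order of the first two factors does not matter, so the expected difference is 0 for every pC. Independence is used only to get figures. The equality holds under any within-subject dependence, provided that order has no effect.

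**2. Rejection rate of the planned test.** The design has 8 subjects per sequence (protocol section 4). Enumerating the two-sided Fisher test at 5% for 8 v 8 over all common event rates, the largest rejection probability is 2.13%, at a rate of 50%. This is the size of the test under a true null. It does not increase with the effect of AL+AQ.

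**3. Illustration with assumed rates.** Take AL at 5%, AQ at 10% or 35%, and AL+AQ at 50% or 70%. Only the 35% has a source: 7 of 20 malaria patients with QTc prolongation on amodiaquine (protocol 13.2), who may differ from healthy volunteers. The last two columns give the power of an exact two-sided McNemar test on 16 pairs with independent periods.

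| AL, AQ, AL+AQ | Any event, each sequence | Fisher 8 v 8 rejects | McNemar AL+AQ v AL | McNemar AL+AQ v AQ |
|---|---|---|---|---|
| 5%, 10%, 50% | 57.3% | 1.99% | 71.3% | 53.9% |
| 5%, 10%, 70% | 74.4% | 0.85% | 97.0% | 91.0% |
| 5%, 35%, 50% | 69.1% | 1.26% | 71.3% | 6.6% |
| 5%, 35%, 70% | 81.5% | 0.35% | 97.0% | 35.0% |

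First row: 1 − 0.95 × 0.90 × 0.50 = 0.5725.

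For smaller effects, with AL+AQ at 20% to 30%, the McNemar power is only 4% to 20% against AL at 5%, and 2% to 11% against AQ at 10%.

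**4. Worked example (assumed counts).** Suppose events occur in 0, 2 and 8 of 16 subjects on AL, AQ and AL+AQ, the 2 being among the 8, and the affected subjects split evenly by sequence.
- By sequence: 4/8 v 4/8, Fisher p = 1.0.
- By regimen, AL+AQ v AL: 8 v 0 discordant, p = 2 × 0.5^8 = 0.008.
- By regimen, AL+AQ v AQ: 6 v 0 discordant, p = 2 × 0.5^6 = 0.031.

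**5. Observation time.** Protocol 6.1.2 and Table 2 schedule follow-up to Day 28 after AL, but to Day 42 after AQ and AL+AQ. A whole-period comparison of AL+AQ with AL would give the combination 14 extra days of scheduled visits.

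**6. Carry-over.** Protocol section 1 gives a half-life of 9 to 31 days for desethylamodiaquine, and the washout is more than 6 weeks. Over 42 days the fraction remaining is 2^(−42/9) = 0.04 to 2^(−42/31) = 0.39. One sequence takes AQ immediately before the combination and the other takes AL.

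**The case against.** The strongest reply is that the plan as a whole is not blind to a QT effect, and this stands. The first sentence of SAP 3.5.3 tabulates AE incidence without a sequence split. Protocol 12.5.2 names QT prolongation, promises tables or graphs and says that clinically relevant abnormalities will be described. Protocol 12.6 relates ECG findings to PK. A reader might infer that a QT effect of the combination cannot appear anywhere, but the documents do not support that. What is missing is any stated contrast of AL+AQ with AL or AQ alone.

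A reader might also infer that the SAP deals with ECG and vital-sign abnormalities only as AEs. It does not say so. It is silent, and the rule that makes them AEs is in protocol 11.2.

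Nor does the as-treated statement in protocol 12.5.2 by itself forbid a sequence table. As treated normally means by treatment received rather than as assigned, and a table by sequence actually received could satisfy it.

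The sequence table has a use. By step 6, up to about 39% of the desethylamodiaquine could remain after 42 days, so a check for carry-over is reasonable. It is the wrong main table.

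Finally, a regimen contrast has limits. AL+AQ is always the third period, so it is confounded with period, and power against AQ may be low (6.6% to 35.0% at the 35% rate). Both points limit what the contrast can prove. Neither makes a by-sequence split answer the question.

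**Conclusion.** The point holds in this form: the stated AE and SAE comparison is by sequence, it reflects only order or carry-over, and it does not address objective 2.3b. SAP 3.5.3 also specifies no summary of ECG or vital signs for an endpoint that the SAP lists.

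The zero expected difference rests on the design alone, given no order or carry-over effect. The 2.1% ceiling adds only 8 subjects per sequence and a two-sided test (the SAP does not state sidedness). The power figures and the worked example are illustrative, because they rest on assumed event rates and independent periods.

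The consequence is modest. Safety is a secondary objective in a 16-subject PK study, and the data for regimen tables are collected in every period. The risk is that a comparison with no bearing on the combination is read as evidence about it.

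**What to change.** Amend SAP 3.5.3 as follows.
- **Assignment.** Assign each AE and SAE to the regimen of the period in which it starts: from the first dose of that period to the first dose of the next, or to the last follow-up visit for Visit 4. Report AEs and SAEs for AL, AQ and AL+AQ.
- **Comparison.** Compare AL+AQ with AL and with AQ within subject, giving the discordant counts and the exact McNemar test. Use a common Day 0 to 28 window for the AL contrast, because AL follow-up ends at Day 28.
- **ECG and vital signs.** Summarise change in QTc, heart rate and blood pressure from Day -1 of the same period by regimen. Give the within-subject difference, AL+AQ minus alone, with its confidence interval.
- **Sequence table.** Keep it as a supplementary check for order or carry-over.
- **Limitation.** State that AL+AQ is always the last period, so the regimen contrast is confounded with period.

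The cost is a short rewrite of SAP 3.5.3 and table shells for AEs by regimen and for ECG and vital signs. No new data, visits or subjects are needed.
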